We hypothesize that negative information in WM in MDD patients will attenuate updating based on the disengagement hypothesis (Koster et al., 2011; Southworth et al., 2017) and that MDD patients have more difficulty in ignoring negative information (less distractor resistance). Moreover, we hypothesize that MDD patients will show improved performance when asked to remember negative information. We expect these difficulties to be accompanied by increased rumination and we expect MBCT to normalize these findings.

Statistical Analysis WMUIET To answer our research question, we will employ generalized mixed effects models with correct choice as dependent variable. We will build the following models: (a) A model for the update trials; (b) a model for the Ignore trials; and (c) an omnibus model encompassing update and ignore trials to compare the relation between update and ignore processes. All models include the subjects as a random effect and will be constructed using a maximal fitting approach with random slopes and intercepts for all the non-correcting independent variables with more than one level (Barr, 2013; Barr et al., 2013).

Model (a) on update trials will include the within subject factors 'Emotion of first set' (2 levels: neutral/sad) and 'Emotion of second set' (2 levels: neutral/sad). Note that in this model the first set must be updated by the second set (thus the second set must be remembered) to come to a correct answer.

Model (b) on ignore trials will include the within subject factors 'Emotion of first set' (2 levels: neutral/sad) and 'Emotion of second set' (2 levels: neutral/sad). Note that in this model the second set must be ignored (thus the first set must be remembered) to come to a correct answer.

Moreover, when significant main effects of emotion for the second set for update trials and of the first set for ignore trials were found, we will assess whether these were indeed due to specifically the update or ignore process respectively by incorporating the no-interference trial and Type of Trial (no-interference/interference) as additional factor in the model.

Furthermore, to investigate the the within-subject relation between the update and ignore trials, an omnibus model will be constructed combining both update and ignore trials with the additional factor Type of Trial (Update/Ignore).

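### The working-memory omnibus model appears to code emotion by set position, whose role swaps between update and ignore trials, so its Type of Trial × Emotion terms do not compare updating with ignoring

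*SAP*

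**What the plan says.** Under Statistical Analysis WMUIET the SAP plans three accuracy models: (a) for update trials, (b) for ignore trials, and (c) "an omnibus model encompassing update and ignore trials to compare the relation between update and ignore processes".

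The first two share the same position-based factors: "Model (a) on update trials will include the within subject factors 'Emotion of first set' (2 levels: neutral/sad) and 'Emotion of second set", and likewise "Model (b) on ignore trials will include the within subject factors 'Emotion of first set' (2 levels: neutral/sad) and 'Emotion of second set". The Task variables section also defines accuracy by the emotion of the first presentation, the emotion of the second presentation and trial type.

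The SAP spells out that the roles differ. For update trials, "the first set must be updated by the second set (thus the second set must be remembered"). For ignore trials: "Note that in this model the second set must be ignored (thus the first set must be remembered) to come to a correct answer".

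For the third model, "an omnibus model will be constructed combining both update and ignore trials with the additional factor Type of Trial (Update/Ignore"). Nothing is said about recoding emotion by role or about a contrast that matches roles across trial types.

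The hypotheses just before this section have negative information attenuating updating and being harder to ignore, whereas "we hypothesize that MDD patients will show improved performance when asked to remember negative information".

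**The concern.** Model (c) is the one named for comparing the two processes. The background to the task asks whether updating and ignoring reflect one disturbed mechanism or different ones. A Type of Trial × Emotion interaction is the natural place to look for a difference.

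Under position coding, Type × First-set contrasts a sad set to be discarded (update) with a sad set to be remembered (ignore). Type × Second-set does the reverse. Neither compares updating with ignoring. Each position main effect averages a target effect with an interference effect and can cancel to nothing.

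If the SAP's directional hypotheses are right, both interactions will differ from zero even when one shared mechanism produced the data. At stake is the conclusion on how updating and ignoring of negative information differ, together with the reading of any Type × Emotion term crossed with Group, IDS-SR or brooding.

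**Working it through.** **Inputs from the SAP.** The roles of the sets and the direction of the hypotheses are as set out above. There are 12 trial types of 20 trials: (4 + 4 + 2 + 2) × 20 = 240, which reproduces the stated total. Eight of these are interference types, giving 8 × 20 = 160 trials for the update–ignore comparison. Alpha is 0.05. Planned inclusion is 200 with 15% drop-out, so 200 × 0.85 = 170.

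**Algebra.** Let the two processes be identical: in both trial types, logit(p) = a + bT × (sad target) + bD × (sad interfering set).

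| Emotion effect of | Update trials | Ignore trials | Ignore − update | Mean over types |
|---|---|---|---|---|
| First set | bD | bT | bT − bD | (bT + bD)/2 |
| Second set | bT | bD | bD − bT | (bT + bD)/2 |
| Target set | bT | bT | 0 | bT |
| Interfering set | bD | bD | 0 | bD |

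The first two rows are position coding and the last two are role coding. The Type × First × Second term is not affected.

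With bT = +0.2 and bD = −0.2:

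- Position coding: Type × First = 0.2 − (−0.2) = +0.4, Type × Second = −0.4, and both main effects are (0.2 − 0.2)/2 = 0.
- Role coding: main effects +0.2 and −0.2, both Type interactions 0.

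With bT = bD = 0.2, both Type interactions are 0 under either coding, so there is no artefact.

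**Simulation.** The SAP gives no effect sizes, variances or accuracy, so these are assumed: logit intercept 1.4 (about 80% correct), random-intercept SD 0.7, random-slope SD 0.2, 20 trials per cell, 1,000 runs. Two-sided t-tests on each subject's accuracy contrasts stand in for the planned mixed model. The two processes are identical in every scenario, so every rejection is a false update–ignore difference. Cells give Type × First / Type × Second under position coding.

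| bT, bD (logit) | N = 100 | N = 170 |
|---|---|---|
| 0, 0 | 5.7% / 5.3% | 4.7% / 4.4% |
| 0.05, −0.05 | 24% / 22% | 33% / 34% |
| 0.1, −0.1 | 65% / 63% | 87% / 87% |
| 0.2, −0.2 | 99.7% / 100% | 100% / 100% |
| 0, −0.1 | 23% / 23% | 35% / 35% |
| 0, −0.2 | 66% / 65% | 87% / 87% |
| 0.2, 0.2 | 5.3% / 4.9% | 5.1% / 4.0% |

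The role-coded tests (Type × Target, Type × Interfering) reject in 3.5% to 6.4% of runs throughout.

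**Limit of the role-coded test.** Suppose a sad second set also has an effect q of its own, whatever its role. The interfering-set effect is then bD in update trials and bD + q in ignore trials, so Type × Interfering = q, not 0. With 150 patients, bT and bD at ±0.2 and q = 0.2, the role-coded test rejects in about 85% of runs. With all three at 0.1 in size, it rejects in about 32%. These sizes are assumed too.

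**The case against.** Several counter-arguments carry weight.

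- **The coding is inferred.** The SAP writes no omnibus formula. Position coding follows from adding one factor to models (a) and (b) and from the Task variables section. It is the only coding offered, but it is a reading.
- **No information is lost.** With all interactions fitted, position and role coding are re-expressions of the same eight cells, and role-aligned contrasts can be taken from the fitted model. This stands. The fault lies in which terms are tested and how they are read.
- **The authors know the roles.** The no-interference follow-up names the second set for update trials and the first set for ignore trials, which are the two targets. That pairing is not carried into model (c).
- **The SAP never says that a significant Type × Emotion term means different mechanisms.** True. Its one-or-two-mechanisms question is framed partly by added explanatory value for rumination and symptoms, which a difference in mean effects would not settle under either coding. The stated purpose of (c) is still to compare the two processes, and the position terms do not do that.
- **Post-hoc simple effects are planned.** Within a trial type they have clear roles, but they return models (a) and (b) and do not test update against ignore.
- **Role coding is not assumption-free.** This stands, as the working shows.

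A reader might infer three stronger things that the SAP does not support. First, that the interactions must be non-zero: this needs bT and bD to differ, which is hypothesised, not known. Second, that all interactions with Group, IDS-SR or brooding are invalid: the SAP reads a significant covariate interaction as some relation with emotion-dependent processing, and that reading can hold under position coding. Third, that aim (iii) rests on model (c) alone: the scores are also added to (a) and (b), where roles are unambiguous.

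**Conclusion.** The point holds in conditional form. As described, model (c) yields Type × Emotion terms equal to ±(bT − bD) when updating and ignoring are identical. The comparison it is named for is therefore not made by its own terms whenever sad targets and sad interference act differently, as the SAP expects. If the two effects are equal, there is no artefact. Type × Emotion terms crossed with Group, IDS-SR or brooding cannot be read as update–ignore differences, although they may still show an emotion-dependent relation.

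The algebra needs no assumed sizes beyond additive target and interference effects. The rejection rates do: where bT and bD differ, they run from 22% to 100% over the scenarios tried.

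This should be fixed before analysis, but it concerns a secondary task. Models (a) and (b), data collection and the primary mediation analysis are untouched.

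**What to change.** - In model (c), replace the position factors by Target emotion (second set in update trials, first set in ignore trials) and Interfering emotion (first set in update trials, second set in ignore trials), fully crossed with Type of Trial. Alternatively, keep the position factors and prespecify the equivalent role-aligned contrasts from the same fitted model.
- Name Type × Interfering emotion as the update–ignore comparison.
- For the aim that the two influences are related to each other, report the by-subject correlation between the interfering-emotion slopes in update and in ignore trials.
- Read terms that cross Type, Emotion and Group, IDS-SR or brooding in the role-coded form only.
- State as a limitation that role, position and trial type are aliased: any two determine the third, so the role-coded Type interaction assumes no separate emotion-by-position effect.

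The cost is SAP wording and a recode of two variables, with the same number of model terms and no new data. Models (a) and (b) stay as they are.

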Figure 3. Instrumental training. To centre the cursor, participants click in a central square. The experiment consists of a block with exclusively instrumental approach trials ($n=120$) and a block with exclusively withdrawal trials ($n=120$). In approach trials (top), participants chose whether to move the cursor towards the mushroom and click inside the blue frame onto the mushroom (go), or do nothing (nogo). In withdrawal trials, they instead moved the cursor away from the mushroom and clicked in the empty blue frame (go) or did nothing (nogo). Outcomes are presented immediately after go actions, or after 1.5 seconds. Per block there are 3 “good” and 3 “bad” instrumental stimuli. Participants play each block ones per testing day. Instrumental stimuli are different for both blocks and both days. **Pavlovian training.** Participants passively view stimuli and hear auditory tones, followed by wins and losses. There are five fractal/tone combinations. Each combination is displayed 12 times in the first block and another 6 times in the second block. **Pavlovian-instrumental transfer.** Participants respond to the instrumental stimuli trained during the instrumental training stage, with Pavlovian stimuli tiling the background. No outcomes are presented, but participants are instructed that their choices count towards the final total. No explicit instructions about the contribution of Pavlovian stimuli towards the final total are given.

2. The working memory update ignore emotion task (WMUIET)

The WMUIET (see Figure 4) contains black and white pictures of sad and neutral emotional faces. The task assesses the influence of emotional information on distractor resistance (ignore) and update capacity of working memory with (emotional) faces as target stimuli. Each trial contains three distinct phases separated by three delay periods.

First set of faces

Participants will be instructed to remember both the place of presentation and the face of two simultaneously presented black and white photographs when, and only when, the letter “T” (= target) appeared in the middle of the screen. Each presented set of photographs always contains two faces with the same emotion (neutral or sad).

Second set of faces

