In the second set, again two black and white pictures of faces will be presented. In total, there are four positions (top left/right, bottom left/right) and the first set always contains opposite positions compared to the second set, so that all four positions have shown a face once in every trial. In the second set, either a “T” or a “+” is presented in the middle of the screen. A “T” (= new Target) again indicates that this set of faces needs to be remembered (= update trial). A “+” (= distractor) indicates that the second set can be ignored (ignore trial). The participants are instructed that only the last target (“T”) set has to be remembered. Thus, the second set determines whether a trial consists of an ignore or update trial.

Probe phase

In the third phase, the probe phase, one face of the last target set is presented, and subjects will be asked to indicate at which position this face was presented in the last target-set with the D, K, C or M key on the laptop keyboard (see Figure 4).

No-interference (NI) trials - controls

In addition to normal ignore and update trials, the task also includes control, or so called no-interference, trials. In these trials, one of the representations does not consist of faces but of blank

rectangles. Therefore, only one set of faces is presented and should be remembered and there will be no influence of update or ignore functions of the working memory. In the update trials, the first set is blank, in the ignore trials the second set because these sets were not the final target sets in normal trials.

Possible combinations

Consequently, the task consists of 12 different types of trials. Four types of trials in both the ignore and update trials (sad → update: sad; sad → update: neutral; neutral → update: sad; neutral → update: neutral and sad → ignore: sad; sad → ignore: neutral; neutral → ignore: sad; neutral → ignore: neutral), two types of no interference ignore trials (neutral → blank; sad → blank) and two types of no interference update trials (blank → neutral; blank → sad). Each of these types consist of 20 trials, so there are 240 trials per participant.

Task variables

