Accuracy will be measured as a correct or a false answer, so a dichotomous variable will be created, and reaction time is measured as a numeric variable. Thus, this task enables us to measure accuracy and reaction time as a function of emotion of the first presentation (3 levels: sad/neutral/NI-update), emotion of the second presentation (3 levels: sad/neutral/NI-ignore), and trial type (2 levels: update-ignore). Note, that this is not a full factorial model with respect to the no interference trials, because these trials only contain one emotion presentation.

[figure not shown]

Figure 4. Working Memory Update/Ignorance Emotion Task. Subjects are instructed to remember the *last* set of faces with a T presented in between and forget about all the earlier presented faces and to-be presented faces without a T in between. In the ignore (distractor resistance) trials, top row, subjects are supposed to remember the target set while interfering information is displayed in the ignore phase. In the depicted case, neutral faces have to be kept in working memory while resisting the sad distractor faces. Whether inhibiting the sad information from working memory was successful is tested in the probe phase, where subjects have to indicate the position where the presented probe face (always from the target set) was presented. In the update trials (2nd row), subjects are supposed to update the first target set with a new target set. In the probe phase, it is tested whether this updating was successful. In the depicted trial subjects are supposed to update a set of sad faces with neutral faces. As a control condition, no interference trials are used with either a blank screen before or after presentation of one set of faces to act as a control condition for ignore and update trials respectively (3rd and 4th row).

Update and distractor resistance capacity of working memory in MDD

Depressed individuals have difficulty in (i) inhibiting negative information from entering working memory (ignoring) (De Lissnyder et al., 2010; Goeleven et al., 2006; Joormann, 2004; Joormann & Gotlib, 2010), and (ii) removing negative information from working memory (updating) (Joormann &

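### In the working-memory omnibus model, Type of Trial is confounded with how long the target is held, so Type effects without an emotion term need the no-interference controls

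*SAP*

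**What the plan says.** Statistical Analysis WMUIET plans three accuracy models. Model (a) takes update trials, where "the first set must be updated by the second set (thus the second set must be remembered"), and model (b) takes ignore trials, where "the second set must be ignored (thus the first set must be remembered"). Each has two emotion factors with two levels, neutral and sad. Model (c) is "an omnibus model encompassing update and ignore trials to compare the relation between update and ignore processes", and its specification is that "an omnibus model will be constructed combining both update and ignore trials with the additional factor Type of Trial (Update/Ignore").

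The task description fixes the order as first set, second set, probe: "Each trial contains three distinct phases separated by three delay periods". It gives no durations.

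The task also has NI trials, in which one set is replaced by blank rectangles. The section on these controls says: "In the update trials, the first set is blank, in the ignore trials the second set". The analysis section uses them only as a follow-up. If the emotion of the target set has a significant main effect in update or ignore trials, that effect is examined "by incorporating the no-interference trial and Type of Trial (no-interference/interference) as additional factor in the model".

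Group is then added as a three-level factor. In patients, IDS-SR and brooding scores are added separately to the models already described. Every significant interaction with one of these scores is to be taken as a link with emotion-dependent working-memory processing.

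**The concern.** Model (c) is the only one of the three in which the position of the target differs between the trials being compared, and it is specified without the controls that match on position. If accuracy falls with a longer hold, the Update/Ignore factor picks up that fall even when updating and ignoring cost the same.

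The same applies to differences between people. If patients, or people who brood more, lose faces faster over a longer hold, a Group × Type or brooding × Type interaction appears with no specific updating or ignoring problem behind it. The SAP's reading rule would then label the brooding or IDS-SR result as emotion-dependent processing, although the term contains no emotion factor. The SAP asks whether updating and ignoring reflect one disturbed mechanism or two, so such a result would bear directly on its conclusions.

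**Working it through.** **Trial count.** The SAP states 240 trials per participant: 12 types × 20 = 240, which reproduces. Update and ignore have 4 × 20 = 80 interference trials each. NI-update and NI-ignore have 2 × 20 = 40 each, 80 in all.

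**What each contrast estimates.** On the logit scale let *b* be a person's level, *c_u* and *c_i* the costs of updating and ignoring, and *r* the extra loss when the target is the first set.

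| Trial | Target | Expected logit |
|---|---|---|
| Update | second set | b − c_u |
| Ignore | first set | b − c_i − r |
| NI-update (first set blank) | second set | b |
| NI-ignore (second set blank) | first set | b − r |

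- Type in model (c): (b − c_u) − (b − c_i − r) = (c_i − c_u) + r.
- Same contrast in NI trials: b − (b − r) = r.
- Type × Interference: (c_i − c_u) + r − r = c_i − c_u.
- Type × target emotion: r cancels if it is equal for sad and neutral faces. Only a sad-minus-neutral difference in r remains.
- Within (a) or (b) the target position is constant, so r does not distinguish the cells.

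The cancellation in the third line assumes that retention loss is additive on the logit scale and equal with and without interference.

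**Type main effect (illustration).** The SAP gives no accuracy or effect size for this task. Assumed: update accuracy about 85%; equal mean costs of 0.5 logit; between-person SDs of 0.7 (level), 0.3 (retention) and 0.3 (each cost); person-level empirical logits; two-sided 5% test; 1,000 replicates. N = 174 is the SAP's required sample size, which was calculated for the mediation analysis.

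| r (logit) | Accuracy, update vs ignore | Type significant | Type × Interference significant |
|---|---|---|---|
| 0 | 84.6% vs 84.6% | 5% | 6% |
| 0.1 | 84.6% vs 83.2% | 48% | 6% |
| 0.2 | 84.6% vs 81.8% | 96% | 7% |
| 0.3 | 84.6% vs 80.2% | 100% | 5% |

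The estimated Type effect equals r. At r = 0.2 the rate is 80% for N = 100 and 98% for N = 200. Type × target emotion stays at about 4% to 7% when r is the same for both emotions. At N = 174 and r = 0.2 it rises to 29% if the loss is 0.1 logit larger for sad faces.

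**Group × Type (illustration).** Assumed: 100 patients, 50 controls, 80 interference and 40 NI trials per type, and the same accuracy levels. *No variation* means that retention and costs do not vary between people.

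| Scenario | Type, no NI: no variation | Type, no NI: SDs 0.3 | NI-adjusted: no variation | NI-adjusted: SDs 0.3 |
|---|---|---|---|---|
| Patients lose an extra 0.2 logit by retention only | 65% | 36% | about 5% | about 5% |
| True 0.2-logit ignoring deficit, no retention effect | 68% | 36% | 23% | 19% |

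The SD of the NI-adjusted contrast is 1.9 times that of the unadjusted one with no variation, and 1.4 times with SDs of 0.3.

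**Which blank trial controls which type.** The controls section pairs blank-first with update and blank-second with ignore. The Figure 4 caption says that a blank before or after the faces serves "to act as a control condition for ignore and update trials respectively", which is the reverse. Under the caption's pairing the NI contrast would be −r instead of r, and subtracting it would double the retention effect.

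**The case against.** The strongest reply is that the SAP's questions about this task concern negative information, so the terms that matter are Type × Emotion, where an equal retention loss cancels. The directional hypotheses about sad faces can be tested in models (a) and (b), where target position is fixed. Both points stand, and they narrow the concern to Type effects without an emotion term. They do not remove it, because the reading rule covers every significant covariate interaction.

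A reader might infer that the whole task analysis is confounded, or that the 80 NI trials go unused. The SAP supports neither. The NI trials do enter the follow-up of models (a) and (b), although conditionally. Task variables also lists NI levels beside the update/ignore factor, so the authors may have meant them for model (c) too. The specification of (c) does not say so, and it builds on emotion factors with two levels.

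A reader might also infer that an NI-based model should replace (c). It should not. NI trials have no non-target emotion, and that factor carries the ignoring and disengagement hypotheses.

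The loss of precision is a fair objection, as the second scenario above shows. The rates also rest on assumed values, two groups where the SAP plans three, and simple tests in place of the planned mixed model. The caption conflict is editorial: the controls section gives its pairing with a reason, and the figure is not available.

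**Conclusion.** The point holds for a limited set of terms: the Type main effect in model (c) and its interactions with Group, IDS-SR or brooding that contain no emotion factor. As planned, these cannot separate an update-ignore process difference from a retention effect, and the last two should not be read as emotion-dependent processing. Type × Emotion terms are at risk only if faces of one emotion are lost faster than the other. Models (a) and (b) are not affected.

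The structural part follows from the order of events; that the interval is longer is an inference, since no timings are stated. How large the distortion is depends on a retention loss that the SAP does not give. A loss of 0.1 to 0.3 logit produces spurious Type effects in 48% to 100% of studies at N = 174, and no loss produces none beyond the nominal 5%. This is a secondary task, and the primary mediation analysis is untouched.

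**What to change.** - Keep model (c) with both emotion factors for the emotion hypotheses.
- Add, unconditionally, a companion model on all 240 trials with Type (update/ignore) × Interference (interference/NI) × target emotion. These factors cross fully: four interference cells of 40 trials and four NI cells of 20, so 160 + 80 = 240.
- Take any claim about a general update-ignore difference, or its relation to Group, IDS-SR or brooding, from Type × Interference and its interactions in that model.
- Limit the reading rule for covariate interactions to those that include an emotion factor.
- Reconcile the Figure 4 caption with the controls section on which blank trial belongs to which type.

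The cost is SAP wording and one more model on trials that the task already includes. The adjusted contrast is clearly less precise (SD about 1.4 to 1.9 times larger under the assumptions above). The SAP should say that power for these general Type contrasts is lower, and that a non-significant result is not evidence that updating and ignoring are equally affected.

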We will assess whether there are differences between healthy controls (HC) and remitted and currently depressed MDD patients by incorporating a factor Group with three levels.

To further answer whether the update and ignore processes are related to rumination and/or depressive symptoms we will add these scores separately to the models described above with only the MDD patients. Any significant interaction with one of these covariates would indicate a relation between emotion dependent WM processing and rumination or depressive symptom severity.

We will report effects significant at an alpha-level of $<.05$. Any significant higher order interactions will be analysed using post-hoc simple interactions for ease of interpretation.

Control analyses WMUIET

As sensitivity analyses we will conduct a number of control analyses that confirm the robustness of the results: we will assess the lack of effect of covariates of no interest, including age and gender.

3. Weekly self-report questionnaires

The weekly self-report questionnaires will be administered after each MBCT session (8 times) and on a weekly basis in the wait-list control group. We will use these measurements for exploration of the (variation in the) timing of individual change processes.

References

Barr, D. J. (2013). Random effects structure for testing interactions in linear mixed-effects models. *Front Psychol*, 4, 328. <https://doi.org/10.3389/fpsyg.2013.00328>

Barr, D. J., Levy, R., Scheepers, C., & Tily, H. J. (2013). Random effects structure for confirmatory hypothesis testing: Keep it maximal. *J Mem Lang*, 68(3). <https://doi.org/10.1016/j.jml.2012.11.001>

Cladder-Micus, M. B., Speckens, A. E., Vrijen, J. N., T. Donders, A. R., Becker, E. S., & Spijker, J. (2018). Mindfulness-based cognitive therapy for patients with chronic, treatment-resistant depression: A pragmatic randomized controlled trial. *Depression and anxiety*, 35(10), 914-924.

Dai, Q., & Feng, Z. (2009). Deficient inhibition of return for emotional faces in depression. *Progress in Neuro-Psychopharmacology and Biological Psychiatry*, 33(6), 921-932.

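### The WMUIET rule labels every score interaction as emotion-dependent, but in the omnibus model Type of Trial (Update/Ignore) x score contains no emotion factor

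*SAP*

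**What the plan says.** All of this is in the SAP, under Statistical Analysis WMUIET.

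- Update model: "Model (a) on update trials will include the within subject factors 'Emotion of first set' (2 levels: neutral/sad"), plus the emotion of the second set.
- Ignore model: "Model (b) on ignore trials will include the within subject factors 'Emotion of first set' (2 levels: neutral/sad"), again plus the emotion of the second set.
- Omnibus model: "an omnibus model will be constructed combining both update and ignore trials with the additional factor Type of Trial (Update/Ignore").
- Conditional control step, run only after certain significant emotion main effects: the update or ignore model is extended "by incorporating the no-interference trial and Type of Trial (no-interference/interference) as additional factor in the model".
- Clinical scores: the question is introduced as "To further answer whether the update and ignore processes are related to rumination and/or depressive symptoms", and the method is that "we will add these scores separately to the models described above with only the MDD patients".
- Reading of the result: "Any significant interaction with one of these covariates would indicate a relation between emotion dependent WM processing and rumination or depressive symptom severity".
- Threshold: "We will report effects significant at an alpha-level of" .05. Post-hoc simple interactions are planned for higher-order interactions only.

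Aim (ii) of the task, in the section on update and distractor resistance capacity, concerns negative information specifically.

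**The concern.** The reading rule attaches a conclusion about emotion to any score interaction in any of the listed models. The omnibus model and the control step each bring in a Type of Trial factor that says nothing about whether the faces are sad or neutral. A two-way interaction of that factor with the score averages over the emotion of both sets. Its null hypothesis is that the score relates to accuracy equally in the two kinds of trial.

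Suppose more depressed or more ruminative patients are worse at resisting any distractor, sad or neutral, while their updating is intact. That is a non-emotional explanation, and the plan needs to separate it from its mood-congruent hypothesis. It would make Type of Trial x score significant, and the rule as written would report it as a link with emotion-dependent processing. Nothing elsewhere in the SAP narrows the rule.

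**Working it through.** The SAP gives no figure on this point, so there is none to reproduce. The check has two parts: a count of terms, and an illustration of how often the affected term could be significant.

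**1. Which score interactions contain emotion?** Write E1 and E2 for the emotion of the first and second set. With k within-subject factors, a full-factorial model has 2^k − 1 interactions with the score.

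| Model | Factors | Score interactions | Without emotion |
|---|---|---|---|
| Update | E1, E2 | 2² − 1 = 3 | 0 |
| Ignore | E1, E2 | 2² − 1 = 3 | 0 |
| Omnibus | E1, E2, Type | 2³ − 1 = 7 | 1 (Type x score) |

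The remaining 6 omnibus terms contain E1, E2 or both. If scores are also added to the control model, Type of Trial (no-interference/interference) x score is emotion-free in the same way.

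**2. What does Type x score respond to?** Let ignore accuracy fall by b logit per SD of the score in all four emotion combinations, with no change in updating.

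- Type x score: mean over ignore cells minus mean over update cells = (4 × (−b))/4 − 0 = −b.
- E1 x score: mean over sad-first cells minus mean over neutral-first cells = (2 × (−b) + 2 × 0)/4 − (2 × (−b) + 2 × 0)/4 = 0. E2 x score and all the higher-order terms are 0 likewise.

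If instead the deficit is the same in both trial types, Type x score is also 0. The deficit is then a score main effect, which the rule does not count.

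**3. How often would Type x score be significant?** From the SAP: 20 trials per trial type and four interference types each for update and ignore, so 80 trials of each. Assumed: 170 patients (close to the 174 derived for the mediation analysis, since none is given for this task), accuracy near 80%, two-sided 0.05, and a between-patient SD of the ignore-update difference (s) of 0.5 or 1.0 logit.

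Hand approximation:

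- Sampling variance of one cell logit: 1/(20 × 0.8 × 0.2) = 0.3125.
- Sampling variance of the ignore-update difference: 2 × 0.3125/4 = 0.156.
- SE of the slope on the standardised score: √(s² + 0.156)/√170. For s = 0.5 this is √0.406/13.04 = 0.049. For s = 1.0 it is √1.156/13.04 = 0.082.
- Probability of significance ≈ Φ(b/SE − 1.96). For b = 0.10 and s = 0.5: Φ(2.05 − 1.96) ≈ 53%. For b = 0.10 and s = 1.0: Φ(1.21 − 1.96) ≈ 23%.

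Simulation of the same setting, using per-patient empirical-logit contrasts and no emotion x score effect:

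| b (logit per SD of score) | s = 0.5 | s = 1.0 |
|---|---|---|
| 0.05 | about 15% | about 8% |
| 0.10 | about 52% | about 24% |
| 0.15 | about 81% | about 42% |
| 0.20 | about 97% | about 65% |

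Repeat runs move these by a few points, and one gave 43% instead of 52%. With 100 patients and s = 0.5, the effects 0.10, 0.15 and 0.20 give about 30%, 61% and 84%. Each emotion-containing term stays near 5% throughout. With a deficit equal in both trial types, Type x score is significant in about 4%.

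**The case against.** The strongest reply is that the reach is small. Aim (ii) is tested directly by the update and ignore models, where the rule is correct. The omnibus model serves a different purpose, comparing updating with ignoring, and the sentence introducing the scores asks about those processes without mentioning emotion. Type of Trial x score is a legitimate answer to that question. All of this stands. It locates the fault in the conclusion attached to the term, not in the model or the test.

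It can also be said that the omnibus formula is not written out; the SAP commits to all main effects and interactions only for the PIT models. That is true. But a factor added to compare the two processes, with scores entered and their interactions read, makes Type of Trial x score the natural term to fit. For the control model the inference is weaker, because that step is conditional and the SAP does not say specifically that scores enter it.

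A reader might infer that the rule cannot separate a general cognitive deficit from an emotional bias at all. The SAP does not support that. A deficit common to both trial types is a main effect and does not trigger the rule. Only a deficit that differs between ignoring and updating is mislabelled, and only through the emotion-free term.

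A reader might also take the percentages as an inflated type I error. They are the power to detect a real Type of Trial x score relation, which would then be given the wrong name.

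Post-hoc simple interactions do not help, since they are planned for higher-order terms and do not alter the reading of a two-way term. An analyst might interpret the term correctly when reporting, but the written rule directs otherwise.

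**Conclusion.** The rule is wrong as written for one of the 7 score interactions in the omnibus model, and for the corresponding term in the control model if scores are added there. It is right for all score interactions in the update and ignore models and for the other 6 omnibus terms. The count rests on a full-factorial reading of the omnibus model.

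How often the mislabelling would occur cannot be settled from the SAP. The range of 8% to 97% depends on effect sizes, accuracy, between-patient spread and a patient number that the SAP does not fix for this task. It shows that the error is possible, not how likely it is.

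The consequence is confined to the interpretation of a secondary experimental task. The mediation analysis, the growth-curve treatment effect, the sample size and data collection are untouched. It is worth correcting because the prespecified conclusion does not follow from the term.

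**What to change.** Reword the interpretation sentence under Statistical Analysis WMUIET so that only interactions containing both the score and at least one Emotion factor (for example score x Emotion of first set, or score x Emotion of second set x Type of Trial) count as evidence of a relation with emotion-dependent processing. Add that Type of Trial (Update/Ignore) x score is reported separately, as an emotion-independent difference between updating and ignoring in their relation to the score; this answers the general question in the preceding sentence. Write out the omnibus formula, and state whether scores enter the no-interference model; if they do, read its Type of Trial x score term the same way.

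The cost is a sentence or two of SAP text, with no new data or model. Fewer terms can then support the emotional reading, which is the intended effect.
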